9.10 OTHER ASPECTS**9.10.1 Ethical approval and informed consent**

The Institutional Review Board (IRB) or Independent Ethics Committee (IEC) of the Regional Ethical Review Board in Stockholm, Sweden (see website www.epn.se/en) has given approval for the SITS-Monitoring Study II (SITS-MOST II) protocol.

SITS-MOST II is an ‘over-arching’ protocol that describes all research and analyses that SITS international is performing with the collected data in the SITS Registry, including this study 1160.235 (a part of the SITS-AF protocol in the SITS Registry).

The appendices in the SITS-MOST II protocol also include a patient information and informed consent form, describing the purpose of the SITS Registry and the reason why the patient is asked to collect their medical data in the SITS registry (see also [Section 10](#)).

The SITS-MOST II protocol and the EC approval document will be archived in the electronic Trial Master File (TMF), see [Appendix 4](#).

9.11 SUBJECTS

Patients with non-valvular Atrial Fibrillation (NVAF) presenting with their first acute ischemic stroke and 18 years or older are study subject (see [Section 9.2](#)).

9.12 BIAS

To assess potential channeling bias baseline characteristics of all patients fulfilling the in/exclusion criteria and were included in SITS-AF registry in the defined time period will be described based on the treatment they receive for stroke prevention in NVAF within 3 months of the index event.

Differences in the patients that are initiated with dabigatran versus patients initiating with VKA, Factor Xa Inhibitors or no oral anticoagulation therapy will be described and set in context to the observed results in the dabigatran treated patient set (see also [Section 9.9](#)).

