9.3 VARIABLES

9.3.1 Exposures

Patient disposition will be provided according to post-stroke treatment (i.e. dabigatran, VKA, factor Xa inhibitors and no OAC therapy). Index event is defined as the acute ischemic stroke that led to hospital admission for eligible patients (baseline visit).

Dabigatran treated patients will be further stratified by newly diagnosed NVAf or prevalent NVAf, prior treatment with anticoagulation including type of anticoagulation therapy (dabigatran, VKA, Factor Xa Inhibitors, no anticoagulation) stroke severity measured by NIHSS score, dose of dabigatran, and timing of dabigatran treatment initiation.

We will describe the timing of dabigatran treatment initiation for secondary prevention of stroke within 3 months after index event in the post-stroke setting. Timing of dabigatran treatment initiation will be summarized as a continuous variable as well as a categorical variable (see [section 9.3.2.1](#)). For patients with dabigatran treatment initiated 28 days or more after index event, further analysis maybe carried out to determine their characteristics. These analyses will be detailed in a separate statistical analysis plan (see [Appendix 4](#)).

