9.5 STUDY SIZE

Approximately 1000 NVAf patients who are treated with dabigatran etexilate within 3 months of index event constitute the main analysis population.

In order to address the further objective on characterisation of NVAf, the analysis population will be broadened to include all European patients with NVAf aged ≥ 18 presenting with their first acute ischemic stroke, regardless of subsequent oral anticoagulation use within the time period until approximately 1000 dabigatran patients are registered in SITS-AF.

Protocol for observational studies based on existing data**BI Study Number 1160-0235****c03412460-01**

Proprietary confidential information © 2017 Boehringer Ingelheim International GmbH or one or more of its affiliated companies

Data will be extracted from the SITS-AF registry from the European dataset for retrospective analysis. The number of patients included in the study is not driven by a formal sample size calculation but rather by available patient numbers, only descriptive or exploratory analyses will be performed for this study.

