9.9 LIMITATIONS OF THE RESEARCH METHODS**Non-interventional study based on existing data**

The quality of a study based on existing data relies on accuracy of recorded data. Important data may not be available. In the absence of randomisation and blinding, it can be difficult to control for bias and confounders.

Selection bias

There is a risk of selection bias at the patient level. Sites might preferentially include "interesting" cases to the SITS study. To minimize selection bias at the patient level, centres were reminded by e-mail every 3 months that all consecutive patients from each site who meet entry criteria must be included in the SITS-Registry.

Lost to follow up

As with all observational studies a loss to follow up can occur. In this study this will affect the patients with a pre-planned follow up (patients initiating dabigatran within the 3 months after the index event). However, considering the short time period of the follow up and the lost to follow up at 3 months in the general SITS Registry being 20%, a similar percentage of lost to follow up is expected in this study as well.

Channeling bias

Protocol for observational studies based on existing data**BI Study Number 1160-0235****c03412460-01**

Proprietary confidential information © 2017 Boehringer Ingelheim International GmbH or one or more of its affiliated companies

Channeling bias can occur due to preferential prescribing in relation to different risks for the events of interest: e.g., if dabigatran would be more often prescribed to higher risk patients compared to other treatments,

In order to assess potential channeling bias patients not receiving dabigatran within 3 months of the index event will be assessed. For example, patients initiating VKAs, other NOACs or no oral anticoagulation therapy will be assessed according to important patient baseline characteristics (e.g. age, sex, comorbidities, stroke and bleeding risk scores, concomitant medications).

Confounding

As in any observational study, confounding may affect the estimation of association between variables and clinical outcome events of interest and statistical techniques such as adjustment for covariates, stratified analyses, matching, etc. can be used to correct for these. But as only major confounders for selected research questions can be captured, unmeasured confounding may remain.

Exploratory analyses

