No formal power calculation has been done for this descriptive study and up to 1,000 patients with an index stroke are planned to be included. Follow-up is limited to three months after index stroke. Subgroup analyses, in particular those restricted to dabigatran patients, are only exploratory in nature. Exploratory analyses are usually not the definitive answer to the question at hand, but can be useful to define hypotheses to be tested in subsequent confirmatory studies.

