4.2 Exclusion criteria

- Documentation that the patient was enrolled or is planned to be enrolled in an investigational clinical trial at the time of the onset of the index event and for the duration of the data collection

5 Information on Data Extraction, Limitations and Bias

Because for most of the objectives we are only using a sample of subjects that initiated treatment prior to dying, having a second stroke or leaving care, we have a selected sample. Therefore, all findings are conditional on subjects actually initiating treatment within 3 months and subjects living and remaining stroke free long enough to initiate treatment. Since this is not a baseline

characteristic, the baseline associations with time to treatment initiation are not generalizable to the population of subjects that would initiate treatment prior to 3-months if they could, as many subjects will die or have second strokes prior to this. For this reason, all findings are hypothesis generating, and would need to be confirmed in a study that includes all subjects which are eligible to initiate treatment prior to 3 months regardless of their actual treatment.

Weaknesses/ limitations

This is a non-interventional study based on existing data, therefore its quality relies on accuracy of recorded data. Important data may not be available. In the absence of randomization, it can be difficult to control for bias and confounders.

Power:

No formal power calculations have been done as this is a descriptive study.

Selection bias

There is a risk of selection bias at the patient level. Sites might preferentially include "interesting" cases to the SITS study. To minimize selection bias at the patient level, centers were reminded by e-mail every 3 months that all consecutive patients from each site who meet entry criteria must be included in the SITS-Registry.

6 Planned Analyses

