▪ Warfarin derivatives
▪ New OAC (NOAC)
• If NOAC
○ Dabigatran
○ Apixaban
○ Rivaroxaban
2h follow up
Systolic Blood Pressure
Diastolic Blood Pressure
NIHSS
24h follow up
NIHSS
Systolic Blood Pressure
Diastolic Blood Pressure
Current Infarct CT/MR
ASPECTS Score CT/MR
Local Haemorrhage CT/MR
Remote Haemorrhage CT/MR
Cerebral Oedema CT/MR
At discharge/ 7d
Diagnosis of NVAf at (previous, at or during hospital stay)
Oral anticoagulation (OAC) at = YES
▪ Warfarin derivatives
▪ New OAC (NOAC)
• If NOAC
○ Dabigatran
○ Apixaban
○ Rivaroxaban
Date & time of OAC start: DD/MM/YYYY, time: clock
OAC at discharge = No
1) Date of foreseen start of OAC if not started during hospital stay
Date: DD/MM/YYYY
Aspirin
mRS Score
NIHSS
Systolic Blood Pressure
Diastolic Blood Pressure
Date of
Dipyridamole
Clopidogrel
Other Antiplatelet

Anticoagulants Oral
Dabigatran
Dabigatran Dose
Date of Dabigatran Initiation
Anti Diabetic Oral
Antihypertensive Oral
Statin
Other
Type Of Stroke
Type Of Stroke Ischemic
Type Of Stroke Haemorrhagic
Date Time Of Death
Cause Of Death
At 3-months
Modified Rankin Scale score
If mRS=6=Dead, date/time of death
Cause of death
Patients with NVAf at discharge/ 7d but patient has not been prescribed Warfarin or NOAC (Dabigatran, Apixaban, Rivaroxaban at
1) Has the patient been prescribed Dabigatran after discharge?
If YES questions below will also be shown.
2) Date of initiation of Dabigatran for stroke prevention in NVAf
Date: DD/MM/YYYY
Dose:
Patients with NVAf has been prescribed dabigatran at discharge
Is the patient continuing the prescribed Dabigatran at 3 months follow up since start of the treatment?
- Yes/ No/ Unknown
If No, date of stop of treatment:
Reason for stop of treatment:
- Has the OAC treatment been changed?
If Yes,
Which treatment:

7.2 Appendix 2

CHADS₂ Stroke Risk Score

CHADS ₂ components	Points
Congestive heart failure	1
Hypertension	1
Age 75 years or older	1
Diabetes mellitus	1
Prior cerebral ischemia (i.e., stroke, TIA)	2
Maximum score	6

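### The dabigatran versus no-anticoagulation channeling contrast counts patients who die before any start as untreated, so part of a baseline difference can reflect early death and not prescribing

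*Protocol*

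**What the plan says.** Protocol 9.12 takes all patients who meet the entry criteria. They "will be described based on the treatment they receive for stroke prevention in NVAF within 3 months of the index event". Differences in those started on dabigatran "versus patients initiating with VKA, Factor Xa Inhibitors or no oral anticoagulation therapy will be described and set in context" with what is seen in the dabigatran set. Protocol 9.3.1 names the groups: "Patient disposition will be provided according to post-stroke treatment (i.e. dabigatran, VKA, factor Xa inhibitors and no OAC therapy". That list has no group for death before a start or for unknown treatment, and neither section sets a landmark time.

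On loss to follow-up, Protocol 9.9 expects about 20% at 3 months and says "this will affect the patients with a pre-planned follow up (patients initiating dabigatran within the 3 months after the index event".

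SAP section 5 recognises that starters are a selected set: "all findings are conditional on subjects actually initiating treatment within 3 months and subjects living and remaining stroke free long enough to initiate treatment". It draws the consequence for baseline associations with time to initiation. It does not mention the comparison in Protocol 9.12, and SAP section 6 contains no channeling analysis.

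The variable list in SAP Appendix 1 (section 7.1) includes the date and time of OAC start, the date and time of death at discharge, and at 3 months "If mRS=6=Dead, date/time of death". For a patient without OAC at discharge, a later dabigatran start is asked about on the 3-month form.

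**The concern.** The treatment groups are defined by what happens after baseline. A patient who dies untreated on day 2 received no OAC and so falls in the no-OAC group, although no prescribing decision need have been made. A dabigatran patient had to live until the start, which may come after day 28. If early deaths have more severe strokes, the no-OAC group looks sicker even when physicians treat comparable survivors alike.

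Protocol 9.9 describes channeling as preferential prescribing and gives this comparison as the way to assess it. At stake is whether a difference is read as prescriber choice when part of it is death before the chance to start.

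A second gap concerns patients discharged without OAC who never have a 3-month form. Their later treatment is unknown, and the plan does not say where they go.

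**Working it through.** **No figure to reproduce.** The study is descriptive: "No formal power calculation has been done for this descriptive study". The size is set by availability: "The number of patients included in the study is not driven by a formal sample size calculation". The check is therefore whether the grouping rule alone can produce a difference.

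**Simple version.** Let dabigatran patients and surviving untreated patients have the same severity distribution (SD 1), let untreated deaths average one SD higher, and let them form a share p of the no-OAC group. The mean difference is p, the no-OAC variance is 1 + p(1 − p), and the standardized difference is p / √(1 + p(1 − p)/2).

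- p = 0.10: 0.10/√1.045 = 0.098
- p = 0.20: 0.20/√1.08 = 0.19
- p = 0.40: 0.40/√1.12 = 0.38

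This overstates the effect. It assumes that dabigatran starters include nobody who later dies, and some will.

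**Fuller version.** I used a simulation of 2 million patients per scenario, with intended treatment independent of baseline severity, so the true channeling is zero. Apart from the 20% loss, no input comes from the documents:

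- 3-month mortality 5%, 10% or 20%
- log-odds of death 0.5 or 1.0 per SD of severity
- death times exponential with mean 20 days, capped at day 90
- intended no-OAC share 20% or 40%, with 30% of intended OAC users on dabigatran
- start times lognormal with median 8 days and log-SD 0.9
- discharge at day 7

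Standardized difference, no OAC minus dabigatran, from deaths only (share of the no-OAC group that died in brackets):

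| Mortality | Log-odds per SD | 20% intended no OAC | 40% intended no OAC |
|---|---|---|---|
| 5% | 0.5 | 0.045 (12%) | 0.022 (8%) |
| 5% | 1.0 | 0.078 (12%) | 0.041 (8%) |
| 10% | 0.5 | 0.077 (22%) | 0.044 (15%) |
| 10% | 1.0 | 0.138 (22%) | 0.077 (15%) |
| 20% | 0.5 | 0.121 (39%) | 0.074 (28%) |
| 20% | 1.0 | 0.212 (39%) | 0.128 (28%) |

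Four of the 12 exceed 0.10. Dabigatran against other OAC stayed within 0.006 of zero, because those patients also had to survive to start.

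**Adding loss.** Suppose lost patients with no start recorded by discharge are counted as untreated.

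- 20% loss unrelated to severity: 0.01 to 0.13, lower than deaths alone in every scenario and above 0.10 in 1 of 12.
- 20% loss with log-odds 0.3 per SD of severity: 0.08 to 0.20, above 0.10 in 8 of 12, and higher than deaths alone in all but the most extreme scenario.
- Loss only, no deaths: 0.00 if unrelated to severity, 0.08 at log-odds 0.3 and 0.13 at 0.5.

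**Testing remedies in the same model.**

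- All dabigatran starters against untreated patients alive with a 3-month form: about −0.01 to −0.13 from deaths only, and about −0.05 to −0.16 with severity-related loss. This is a bias in the opposite direction.
- Both groups restricted to patients alive with a 3-month form: at most about 0.01 in size.
- Patients alive at day 7, classified by OAC status on that day: also at most about 0.01 in size.

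**The case against.** The strongest reply is that little depends on this comparison. It is descriptive, comment 7.1.1 of the ENCePP checklist says that no clinical outcomes are compared by treatment received, and no objective uses it. SAP section 5 already warns about survival and calls all findings hypothesis generating. The SAP also tabulates physicians' own reasons for not planning OAC, and the registry records a foreseen OAC start date at discharge, which partly separates planned starters from the rest. This stands, and it limits the severity. It does not remove the gap, because none of it changes how patients who die untreated are grouped in Protocol 9.12.

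A reader might infer three stronger points that the documents do not support.

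- That the plan puts lost patients in the no-OAC group. No section says so. The registry has an unknown option for OAC, and Protocol 9.7 leaves unknown cases out of baseline percentages. The supportable point is that the rule is missing.
- That loss always adds to the false difference. It does so only if loss depends on baseline risk.
- That the whole channeling check fails. Only the no-OAC contrast is affected to any extent.

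It would also go too far to say that the report will blame prescribers. Protocol 9.12 promises only to describe the differences and put them in context.

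**Conclusion.** The concern holds for one contrast. As Protocol 9.12 and 9.3.1 define the groups, deaths before any start count as no OAC while dabigatran patients are survivors to their start. The dabigatran versus no-OAC difference can therefore arise with no channeling at all. Early deaths alone give about 0.02 to 0.21 in standardized units under the stated assumptions.

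That range is illustrative, because the documents give no mortality figure. The 10% mark in the SAP is set for its own comparisons of timing, reasons and dose, so exceeding it here is a yardstick and not a breach of the plan. The figure of 0.38 from the simple formula should not be taken as the expected size. The direction and size of any effect of loss cannot be stated until the plan says how unknown treatment is classified.

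Severity is minor. The primary analysis of initiation times is untouched.

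**What to change.** In Protocol 9.12, and in a matching new SAP section, report three separate columns in place of the single no-OAC group: died without OAC; treatment unknown (no 3-month form); alive with a 3-month form and no OAC.

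Make the dabigatran versus no-OAC comparison with the same condition on both sides, in one of two ways:

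- restrict both groups to patients alive with a 3-month form; or
- take patients alive at a landmark such as discharge/day 7 and classify them by OAC status at that time.

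Do not set all dabigatran starters against 3-month survivors only, which creates the reverse bias. The first option describes survivors only, and the check above assumed that treatment does not affect survival. The second counts later starters as not yet treated.

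Amend Protocol 9.9 to say that loss also affects the classification of patients discharged without OAC. Confirm too that the 3-month form captures VKA and factor Xa starts after discharge: the items listed in SAP Appendix 1 for these patients ask only about dabigatran, although that list may be incomplete.

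The cost is a few table columns, a short SAP section, one amended sentence and smaller comparison groups. Death dates and OAC start dates are already among the listed variables.

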10. PROTECTION OF HUMAN SUBJECTS

All data entered into the SITS International AF registry are encrypted in order to maintain patient data privacy. The individual patient and its research data is identified by a unique registry identification number. Access to data is strictly controlled by permitting each user a unique username and password. Additionally, each user has restrictions in viewing data sets, depending on their activity role in the database. Each data entry is centrally monitored by internal quality checks, such as automatic range checks and a full audit trail is maintained.

11. MANAGEMENT AND REPORTING OF ADVERSE EVENTS/ADVERSE REACTIONS

According to the European Medicines Agency (EMA) Guideline on Good Pharmacovigilance Practices (GVP), Adverse Event (AE) reporting is not required for Non-Interventional Study (NIS) which is based on secondary data use.

As an observational study, based on existing data, all patient data is de-identified and will be analysed in aggregate. Individual patient safety related information will not be captured during this study. Thus, individual safety reporting is not applicable. Safety reporting will be done cumulatively in aggregate in the study report.

14. APPENDICES

APPENDIX 1: CHADS₂ STROKE RISK SCORE

CHADS ₂ components	Points
Congestive heart failure	1
Hypertension	1
Age 75 years or older	1
Diabetes mellitus	1
Prior cerebral ischemia (i.e., stroke, TIA)	2
Maximum score	6

CHADS₂ score is based on a point system in which 2 points are assigned for a history of stroke or transient ischemic attack and 1 point each is assigned for age 75 years or older, hypertension, diabetes, or clinical heart failure or impaired left ventricular systolic function (generally interpreted as an ejection fraction $\leq 40\%$). A CHADS₂ score of 0 identifies patients at low stroke risk, a score of 1 to 2 identifies patients at moderate stroke risk, and a score greater than 2 identifies patients at high stroke risk [[P06-10925](#)].

APPENDIX 2: CHA₂DS₂-VAS_c STROKE RISK SCORE

CHA ₂ DS ₂ VAS _c score	
Risk factors for stroke and thrombo-embolism in non-valvular AF	
Major risk factors	Clinically relevant non-major risk factors
Previous stroke, TIA, or systemic embolism Age ≥ 75 years	Heart failure or moderate to severe LV systolic dysfunction (e.g. LV EF ≤40 %) Hypertension - Diabetes mellitus Female sex - Age 65-74 years Vascular disease

Risk factor-based approach expressed as a point based scoring system, with the acronym CHA₂DS₂-VAS_c
 
(Note: maximum score is 9 since age may contribute 0, 1, or 2 points)
	
Risk factor	Score
Congestive heart failure/LV dysfunction	1
Hypertension	1
Age ≥75	2
Diabetes mellitus	1
Stroke/TIA/systemic embolism	2
Vascular disease*	1
Age 65-74	1
Sex category (i.e. female sex)	1
Maximum score	9

* Myocardial infarction, complex aortic plaque and PAD

The CHA₂DS₂-VAS_c risk score is based on a point system in which 2 points are assigned for a history of stroke or TIA, or age ≥75; and 1 point each is assigned for age 65–74 years, a hypertension, diabetes, cardiac failure, vascular disease and female sex. On the basis of the risk strata defined in previous guidelines, a CHA₂DS₂-VAS_c score of 0 corresponds to “low risk”, a score of 1 corresponds to “intermediate risk”, and a score of 2 or more corresponds to “high risk” [[R10-5332](#)].

APPENDIX 3: HAS-BLED BLEEDING RISK SCORE

Clinical characteristics comprising the HAS-BLED bleeding risk score		
Letter	Clinical characteristic	Points awarded
H	Hypertension	1
A	Abnormal renal and liver function (1 point each)	1 or 2
S	Stroke	1
B	Bleeding	1
L	Labile INRs	1
E	Elderly (e.g. age >65 years)	1
D	Drugs or alcohol (1 point each)	1 or 2
Maximum score		9

Hypertension is defined as history of hypertension and current uncontrolled systolic blood pressure >160 mmHg. ‘Abnormal kidney function’ is defined as the presence of chronic dialysis or renal transplantation or serum creatinine ≥ 200 $\mu\text{mol/L}$. ‘Abnormal liver function’ is defined as chronic hepatic disease (e.g. cirrhosis) or biochemical evidence of significant hepatic derangement (e.g. bilirubin >2 x upper limit of normal, in association with aspartate aminotransferase/alanine aminotransferase/alkaline phosphatase >3 x upper limit normal). ‘Bleeding’ refers to previous bleeding history and/or predisposition to bleeding, e.g. bleeding diathesis, anaemia, etc. ‘Labile INRs’ refers to unstable/high INRs or poor time in therapeutic range (e.g. <60%). Drugs/alcohol use refers to concomitant use of drugs, such as antiplatelet agents, non-steroidal anti-inflammatory drugs, or alcohol abuse, etc. If a patient is not on VKA the value for ‘labile INRs’ will be set to 0. Further details will be given in the separate statistical analysis plan (see [Appendix 4](#)).

A HAS-BLED score of ≥ 3 indicates ‘high risk’ for AF patients to develop a bleed and some caution and regular review of the patient is needed following the initiation of antithrombotic therapy, whether with VKA or aspirin [[R10-6394](#)].

